4.3.4 Treatment Phase Day 5 (+/- 2 days)

In addition to what is collected daily during the Treatment Phase as per [Table 1](#), whenever possible, sparse PK will be collected on Day 5 (+/- 2 days). Additionally, experimental predictive biomarkers will be collected on Day 5 (+/- 2 days), with the exception of troponin which is only collected at Screening as per [Table 1](#).

4.3.5 End of Treatment or Day 15 (+/- 1 day)

Subjects will complete the End of Treatment (EOT) Visit after their last dose of study drug (if they discontinue drug prior to Day 15) or on Day 15 +/- 1 day after the subject has received 42 doses of study drug as per [Table 1](#). If possible, the subject should return for Post-Dose Follow-up visits on Day 22 (+/- 2 days) and Day 29 (+/- 2 days). If a subject has an EOT visit prior to Day 15, then the Day 15 visit should be done as a telephone visit.

Subjects need to have a SARS CoV-2 antibody test completed no earlier than Day 15, but no later than Day 60 (see Section [6.3.5.4](#)).

4.3.6 Post Treatment Phase (Days 16 +/- 1 day Through 29 +/- 2 days)

4.3.6.1 For Subjects Who Remain in the Hospital

After administration with the study medication ends, the 6-point ordinal scale assessment, daily vital signs, SpO₂, FiO₂, concomitant medications and procedures, and NEWS2 will continue to be collected daily while the patient is in the hospital ([Table 1](#)). AEs/SAEs, should be captured and followed to resolution or stabilization. Clinical safety labs will be collected per protocol on Days 22 (+/- 2 days) and 29 (+/- 2 days). If clinical safety labs, urinalysis, LFTs, and ECGs are collected as per SOC on any days out to Day 29, data that are clinically significant should be entered into the eCRF on Unscheduled Visit assessment pages. Any chest x-rays collected as per SOC from Day 16 through 29 should be entered into the eCRF on Unscheduled Visit Chest x-ray pages.

If the subject is admitted to the ICU, then SOFA2 will be collected upon admission to the ICU and on Day 29 if the subject is still in the ICU. Subjects need to have a SARS CoV-2 antibody test completed no earlier than Day 15, but no later than Day 60 (see Section [6.3.5.4](#)).

4.3.6.2 For Subjects Discharged from the Hospital after Day 15, but Prior to Day 22

If a subject is discharged from the hospital prior to Day 22, when possible, they should return to the site on Day 22 (+/- 2 days) and Day 29 (+/- 2 days) to have the assessments indicated in [Table 1](#) and should receive a follow-up phone visit on Day 60.

If the subject is unable to return for in-person visits on Days 22 and 29 due to COVID-19 restrictions, a phone call should be made to the subject to collect these assessments: 6-point ordinal scale, AEs/SAEs, and concomitant medications and procedures on those visit days (+/- 2 days). Subjects will need to return for at least 1 in-person visit on or before Day 60 to have the Day 29 assessments completed. Subjects need to have a SARS CoV-2 antibody test completed no earlier than Day 15, but no later than Day 60 (see Section 6.3.5.4).

4.3.7 60-Day Safety Follow-up Visit (+/- 15 Days)

If subjects have been able to return for an in-person visit on Day 29, this will be a follow-up safety phone visit. During this contact, the staff will collect the 6-point ordinal scale, collect any new SAEs, update the status of any AE/SAEs that were ongoing since the last visit, and confirm subject mortality status.

If subject has been unable to complete an in-person visit from the time of hospital discharge prior to Day 60, this Day 60 visit should be an in-person visit, and the same assessments that would have been collected at Day 29 should be performed.

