3.2.2 Other Secondary Endpoints

1. Number of subjects with deaths, SAEs, severe AEs, and Grade 3 or 4 laboratory test abnormalities at any time on study. All AEs are from AE/SAE eCRFs. Grade 3 or 4 laboratory test abnormalities are determined from laboratory test values graded using standardized criteria defined in the SAP (e.g., CTCAE) from laboratory test eCRFs.
2. Number and percentage of subjects with severe or life-threatening bacterial, invasive fungal, or opportunistic infections at any time through Day 29 from AE/SAE eCRFs.

3. Number and percentage of subjects with intranasal administration reactions at any time through Day 29 from AE/SAE eCRFs.
4. Proportion of subjects with 250% reduction in eGFR from baseline at any time on study from laboratory test eCRFs.

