4 STUDY PLAN

4.1 Study Design and Duration

This is a double-blind, randomized, multicenter, inpatient (and post-discharge outpatient) evaluation of the safety and efficacy of zavegeptant (BHV-3500) as compared to placebo in the treatment of COVID-19-associated pulmonary disease. The study drug will be zavegeptant or matching placebo, given as 10 mg IN dose every 8 hours (+/- 2 hours) for approximately 14 days (42 doses). The study will randomize approximately 120 subjects in a 2:1 ratio across the two treatment groups (zavegeptant or matching placebo). The randomization will be stratified by age (less than 60 years vs 60 years and older).

After signing informed consent and meeting eligibility criteria, the subject may be immediately randomized and dosed with the double-blind study medication (10 mg or matching placebo) and continue dosing every 8 hours (Q8h +/- 2 hours) up to approximately 14 days (42 doses).

[figure not shown]
For the purposes of this protocol, the start of Visit Day 1 will start when the 1st dose of study drug is administered until 24 hours later. Therefore, depending on the time when the 1st dose of study drug is administered, a visit day may spread over 2 calendar days. The last dose of study drug could be administered on Visit Day 14 but could actually occur on calendar day 15 of the study. The EOT or Day 15 assessments (depending on when subject stops study drug) should be completed after the last dose of study drug, and the subjects should remain in the hospital for a full 24 hours after their last dose of drug if they are to be released.

Randomization will be done through an IWRS that will be accessed by the unblinded research pharmacists or their designees. so that subjects can be dosed as soon as possible following consent and assessment of eligibility criteria. After completion of treatment, subjects will be followed out to Day 60 (+/- 15 days) during the post treatment phase.

This study has a duration approximately 8 weeks from time of Screening and obtaining consent through the Post-Dose Follow-up Visit (Day 60 +/- 15 days).

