Concomitant Medication Collection	X	X	X	X	X		Concomitant medications are captured from first dose of study drug through Day 29.
Concomitant Procedures Collection	X	X	X	X	X		Concomitant procedures are captured from first dose of study drug through Day 29 except for the start of supplemental oxygen which could start within 48 hours of randomization. This data should be captured on the concomitant procedures page.
AE Assessment		X	X	X	X		Non-serious AEs are captured from first dose of study drug through Day 29. Non-serious adverse events should be followed until conclusion or stabilization or reported as SAEs if they become serious. Follow-up is also required for non-serious AEs that

Procedure	Screening Visit Day -2 to Day 1	Baseline Visit (Randomization) Day 1	Days 2 through 14 (+/- 1 day)¹	End of Treatment (EOT) Visit or Day 15 (+/- 1 day)²	Post-Treatment Phase Days 16 (+/- 1 day) through Day 29³ (+/- 2 days)	Day 60 (+/- 15 days)	Comments
							cause interruption or discontinuation of study drug or those that are present at Day 29. Note: For this study, admission and discharge to the ICU should be captured on the Adverse Event eCRF.
SAE assessment	X	X	X	X	X	X	
SAEs are captured any time after signing consent through the Day 60 visit.
 
All SAEs should be followed until resolution or stabilization.

Administer study drug		X	X				
IP is dispensed every 8 hours (+/- 2 hours) during the Treatment Phase for a total of 42 doses.
 
If subjects are discharged from the hospital to home prior to Day 15 they will be discontinued from study drug but continue in the study. Please note that due to the potential for rebound from withdrawal of an immunomodulating agent, subjects who are planning to be discharged should be off of study drug for at least

Procedure	Screening Visit Day -2 to Day 1	Baseline Visit (Randomization) Day 1	Days 2 through 14 (+/- 1 day) ¹	End of Treatment (EOT) Visit or Day 15 (+/- 1 day) ²	Post-Treatment Phase Days 16 (+/- 1 day) through Day 29 ³ (+/- 2 days)	Day 60 (+/- 15 days)	Comments
							24 hours before release from the hospital. If the subject is discharged to a step-down or satellite care facility where they can be monitored for safety, they should continue receiving study drug until completing 42 doses.

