8.3.2 Collection and Reporting Serious Adverse Events

Following the subject's written consent to participate in the study, all SAEs, whether related or not related to study drug, must be collected, including those thought to be associated with protocol-specific procedures. All SAEs must be collected that occur from signing consent and throughout the course of the study up to and including the Post-dose Follow-up Visit Day 60.

All SAEs should be followed to resolution or stabilization.

An SAE report should be completed for any event where doubt exists regarding its status of seriousness.

If the investigator believes that an SAE is not related to the study drug but is potentially related to the conditions of the study (such as a withdrawal of previous therapy or a complication related to study procedure), the relationship should be specified in the narrative section of the SAE Report Form.

SAEs, whether related or not related to study drug, overdose (see Section 8.3.3), potential drug induced liver injury (see Section 8.3.3) and pregnancies (see Section 8.3.4) must be reported within 24 hours of the Investigator becoming aware of the event. The Investigator is responsible for submitting all applicable events to the IRB as per the IRB's reporting requirements. Additionally, the Investigator, or designated staff, is responsible for entering the SAE information into the eCRF and/or system (i.e., event term, start/stop dates, causality, and severity).

Any serious adverse event must be reported immediately or no later than 24 hours after awareness of the event to PPD Pharmacovigilance (PVG). A written description of any serious adverse event, using the PPD SAE report form, must be sent to PPD PVG by facsimile (fax), within 24 hours after awareness of the event:

- North America: [name]
- EU EMEA: [contact]

Due to COVID-19 restrictions for sites, SAE reports may be sent via encrypted email to PPD at: [contact]. The subject line of the email must include **"Biohaven Protocol BHV3500-203."**

If a form is unable to be submitted within 24 hours, the SAE may be reported by telephone via the Safety Hotline Number:

- North America: [name]
- EU EMEA: [contact]

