8.4.1 Collection and Reporting of Non-Serious Adverse Events

The collection of non-serious AE information should begin at the initiation of study drug through Day 29.

Non-serious adverse events should be followed until conclusion or stabilization or reported as SAEs if they become serious. Follow-up is also required for non-serious AEs that cause interruption or discontinuation of study drug or those that are present at Day 29.

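### Deaths and SAEs are collected only up to a final contact allowed from Day 45 to Day 75, so new events between an early contact and Day 60 are lost

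*Protocol*

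**What the plan says.** Section 3.2.2, item 1, defines the safety endpoint as "Number of subjects with deaths, SAEs, severe AEs, and Grade 3 or 4 laboratory test abnormalities at any time on study". It names no end day, whereas items 2 and 3 of the same list stop at Day 29.

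The end of collection is tied to a visit. The SAE row of Table 1 (Section 4.3) states: "SAEs are captured any time after signing consent through the Day 60 visit". Section 8.3.2 says the same: SAEs are collected "throughout the course of the study up to and including the Post-dose Follow-up Visit Day 60". Under Section 4.3.7 that contact also confirms whether the subject is alive.

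The visit has a wide window. Section 4.3.7 is headed "60-Day Safety Follow-up Visit (+/- 15 Days", and Section 4.1 says that "subjects will be followed out to Day 60 (+/- 15 days) during the post treatment phase". The synopsis gives Day 60 as the end of follow-up without the window.

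Table 1 (footnotes 1 and 3) and Sections 4.3.3.2 and 4.3.6.2 also ask discharged subjects who could not attend earlier visits for one in-person visit no later than Day 60.

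**The concern.** A subject whose final contact is on Day 45 has met every follow-up requirement. If that subject dies or has a new SAE on Day 50, nothing in the protocol requires the event to be found. The same event in a subject contacted on Day 75 is collected and counted. The length of observation for the most serious safety outcomes is therefore set by scheduling.

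This is a matter of data collection, so analysis cannot fully repair it. An analysis rule can cut all subjects off at a common day, but it cannot recover an event that nobody asked about. As written, every subject could finish by Day 45, and the latest day with assured complete coverage would then be Day 45. Safety is part of the overall objective in the synopsis, and with 80 and 40 subjects late events will be few, so one or two missed deaths would matter to the description.

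**Working it through.** **Inputs from the protocol.** Final contact at Day 60 ± 15 days (Sections 4.1 and 4.3.7). SAE collection ends at that contact (Table 1, Section 8.3.2). Planned allocation is 80 and 40 (Section 9.1). SAE frequencies are summarised by treatment group, with no exposure adjustment stated (Section 9.3.6).

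**Window.**
- Earliest contact: 60 − 15 = Day 45. Latest: 60 + 15 = Day 75.
- Spread between completing subjects: 75 − 45 = 30 days; ratio 75/45 = 1.67.
- Largest shortfall against Day 60: 60 − 45 = 15 days, and 15/60 = 25%.

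**Assumptions for size.** Let q be the chance of a first death or SAE over Days 45 to 75. The protocol gives no value, so q = 1%, 2% and 5% are shown. The daily hazard is taken as constant, h = −ln(1 − q)/30. Contact days are taken as uniform over 45 to 75 in both arms.

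**Chance shift between arms.**
- SD of the contact day: 30/√12 = 8.66 days.
- SE of the difference in mean contact day: 8.66 × √(1/80 + 1/40) = 1.68 days.
- 95% limit: 1.96 × 1.677 = 3.29 days. The expected difference is zero.
- Shift in the arm difference at that limit, h × 3.29: 0.11 points (q = 1%), 0.22 (q = 2%), 0.56 (q = 5%).

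**Events before Day 60 that are missed.**
- With uniform contact days, the mean time lost before Day 60 is (15²/2)/30 = 3.75 days per subject.
- Expected number missed among 120, about 120 × h × 3.75: 0.15 (q = 1%) to 0.77 (q = 5%).

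**Extreme case.** If every subject in an arm were contacted on Day 45, the arm would lose 1 − √(1 − q) against Day 60: 0.5 points (q = 1%) to 2.5 points (q = 5%), or 0.4 to 2.0 subjects of 80.

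**Effect of the fix.** With every completing subject contacted on Day 60 or later and counting stopped at Day 60, the counted period is the same for all of them and the 30-day spread falls to 0. Sample size, power and alpha do not change.

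**The case against.** Much of the case on the other side stands.

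- **The SAP may set the cut-off.** The protocol leaves statistical detail and further safety analyses to the SAP. A missing counting rule is therefore not an error here. SAE start dates are recorded, so a common cut-off at Day 45 or a time-to-event analysis is possible. This does not answer the collection gap between an early contact and Day 60.
- **Ongoing SAEs are still followed.** Table 1 and Section 8.3.2 require follow-up to resolution or stabilisation. A death on Day 50 from an SAE still unresolved on Day 45 should be captured. The loss is confined to events with new onset after the last contact.
- **Day 45 is already late.** The last of 42 doses falls around Day 14 or 15, about 30 days earlier, and Section 1.3.1 gives a half-life of about 6 hours.
- **The window is disclosed and symmetric.** Section 4.1 states it openly, and it applies to both arms of a blinded trial.

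A reader might go further and infer three things that the documents do not support:

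1. *That the comparison of arms is biased.* Nothing suggests that contact timing differs by arm. It may vary with discharge status, because the in-person visit is due no later than Day 60, but that rule is the same for both groups.
2. *That an arm's event rate moves by 0.5 to 2.5 points.* That needs a whole arm contacted on Day 45.
3. *That the endpoint contradicts itself on severe AEs, because non-serious AE collection "should begin at the initiation of study drug through Day 29".* The collection periods are stated by event type, and the on-study label can be read as each type's own period. The SAP can settle it.

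**Conclusion.** The point holds as a minor one about collection. Completing subjects have a last contact between Day 45 and Day 75, and deaths or SAEs with new onset between an early contact and Day 60 are outside required collection. The consequence is incomplete ascertainment and some noise in a descriptive safety table. For q between 1% and 5%, the chance shift between arms is roughly 0.1 to 0.6 percentage points, and fewer than one event before Day 60 would be expected to be missed among 120 subjects. Both figures rest on the assumed event rate, a constant hazard and uniform contact days. Contacts clustered before Day 60 would raise the number missed. Loss to follow-up would widen the spread further and is not included.

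The primary endpoint (Day 15), the key secondary endpoints (Day 29) and non-serious AE collection (Day 29) are not touched.

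**What to change.** - In Table 1 and Section 4.3.7, require the final SAE and vital-status contact on Day 60 or later, for example with a window of 0 to +15 days, by telephone if need be.
- Keep the required in-person visit, due no later than Day 60, as a separate item, and close it with that call. Without this separation, a subject with no earlier in-person visit would have only Day 60 itself on which to meet both rules.
- In Section 3.2.2, item 1, count deaths and SAEs with onset through Day 60 and list later events separately. Align the synopsis, Section 4.1 and Section 8.3.2.

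The cost is less scheduling flexibility before Day 60 and one short call for subjects seen early.

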4.4 Post Study Access to Therapy

Not Applicable.

5 POPULATION

Individuals entered in this trial will be male and female subjects 18 years of age and older with PCR-documented COVID-19 infection that necessitates hospitalization with supplemental oxygen. The treatment setting for these subjects will include hospitals or institutions where subjects will be treated for symptoms related to COVID-19. Subjects may be recruited through a variety of sources, including referrals from physicians and other health care professionals.

5.1 Number of Subjects

Up to approximately 180 subjects will be screened and up to approximately 120 subjects will be treated with study drug in this study. It is anticipated that enrollment will occur at approximately 2-5 sites in the United States over a period of approximately 4 months.

5.2 Inclusion Criteria

1. Subjects must provide informed consent in accordance with requirements of the study center's IRB or ethics committee, prior to the initiation of any protocol-required procedures.
2. Subjects must agree to provide all requested demographic information (i.e. gender, race).
3. Subjects must be able to read and understand English or Spanish.
4. Subjects must be over the age of 18 years.
5. Subjects must have laboratory-confirmed SARS-CoV-2 infection as determined by PCR-based commercial or public health assay.
6. Subjects must have symptoms that require hospitalization with supplemental oxygen and/or non-invasive ventilation as determined by the admitting physician. The maximum nasal cannula O₂ concentration should be determined by the treating clinician and the limitations of the specific equipment.
7. Subjects must be willing and able to comply with study-related procedures/assessments.

5.3 Exclusion Criteria

1. Subjects in immediate need of invasive mechanical ventilation or extracorporeal membrane oxygenation (ECMO).
2. Subjects with an eGFR of < 30 mL/min, at the Screening Visit
3. Prisoners or subjects who are involuntarily incarcerated
4. Subjects who are participating in any other investigational clinical trial while participating in this clinical trial

5. Subjects who are under the age of 18 years
6. Subjects who are pregnant (all potential female enrollees need to have a negative pregnancy test prior to IP administration)
7. Subjects with multi-organ failure
8. Subjects who have received more than 48 hours of supplemental oxygen prior to randomization
9. Subjects with prior significant pulmonary disease (e.g., severe COPD/ILD/CHF/IPF) are excluded
10. Subjects receiving investigational therapies as part of a formal clinical trial for the treatment of COVID-19. During the course of this study, investigational therapies that may become “standard of care” to treat COVID-19, but are not part of a clinical trial, are allowed.
11. Subjects who are on long-acting CGRP monoclonal antibodies will be excluded including Aimovig® (erenumab), Emgality® (galcanezumab), Ajovy® (fremanezumab), and Vyepti® (eptinezumab). Additionally, the investigational oral CGRP receptor antagonist, atogepant, that is taken daily will also be excluded. Oral CGRP receptor antagonists, Nurtec® ODT (rimegepant) and Ubrelvy™ (ubrogepant) that are typically used PRN infrequently will not be excluded as long the subject was not taking them on a daily basis and does not take them during the current study
12. Subjects who are unlikely to survive for more than 48 hours from the Screening Visit
13. Subjects with any of the following abnormal laboratory values at screening: aspartate AST or ALT greater than 5x ULN or bilirubin greater than 2x ULN
14. Subjects with known active TB, history of incompletely treated TB, suspected or known extrapulmonary TB
15. Subjects with suspected or known systemic bacterial or fungal infections. However, empiric antibiotics are permitted
16. Subjects who have participated in any clinical research study evaluating an IP or therapy within 3 months and less than 5 half-lives of IP prior to the screening visit
17. Subjects with any physical examination findings and/or history of any illness that, in the opinion of the study investigator, might confound the results of the study or pose an additional risk to the subject by their participation in the study

Please see Section [5.4](#) for prohibited medications during the course of the study.

5.4 Prohibited and Restricted Concomitant Medications/Procedures

Investigational therapies as part of a formal clinical trial for the treatment of COVID-19 are prohibited during the course of this study. However, if during the course of this study investigational therapies become “standard of care” to treat COVID-19, they are allowed.

Long-acting CGRP monoclonal antibodies Aimovig (erenumab), Emgality (galcanezumab), Ajovy (fremanezumab), and Vysepti (eptinezumab) are not allowed in the trial. A minimum 30-day washout period for these drugs is appropriate, prior to randomization. Additionally, the investigational oral CGRP receptor antagonist, atogepant, that is taken daily will also be excluded. Oral CGRP receptor antagonists, Nurtec ODT (rimegepant) and Ubelyv (ubrogepant) that are typically used PRN infrequently will not be excluded as long the subject was not taking them on a daily basis and does not take them during the current study.

Prior to the Baseline Visit (randomization), if a subject has been on non-invasive supplemental oxygen for more than 48 hours, they should not be randomized. However, if a subject progresses to requiring mechanical ventilation (invasive or non-invasive) after randomization, they will remain on the study, per the Investigator's judgement.

Subjects with renal impairment who have an eGFR \geq 2. 30mL/min are allowed into the study. Subjects who develop an eGFR $<$ 15mL/min while on the study should be discontinued from the study drug.

